#### 4.1.9.3 *Intra-Subject Dose Escalation*

Intra-subject dose escalation of IACS-010759 (in accordance with the dosing schema in Table 1 and 2) will be permitted provided:

- Subject has completed ≥2 cycles at their current dose level and has not achieved a CR or Cri
- Subject has not experienced any grade 3 or higher non-hematologic drug-related toxicity, and

Subject has not experienced DLT,

- The dose may be escalated by one dose level no more frequently than every 2 cycles.
- The escalated dose level must have been fully evaluated and shown not to exceed the MTD (0 DLT of 3 or ≤1 DLT of 6)

If an intra-subject dose escalation occurs, laboratory monitoring will be increased to weekly during the first cycle of the increase dose.

#### 4.1.9.4 Other Allowable Modifications of Dose Schedules

Other modifications of dose schedules than the above will be allowed within the following guidelines:

- Further dose reductions can be made to keep clinically significant toxicities grade < 2.
   
Dose adjustments by more than 1 dose level at a time (e.g., from cohort 6 dose to cohort 4 dose) can be considered when judged in the best interest of the subject (e.g. severe myelosuppression, lactic acidosis) when the toxicity has resolved. The reason for this reduction will be discussed with the PI or Co-PI and documented in the medical record.
- Treatment interruptions and dose modifications other than the ones mentioned above can be considered after discussion with the PI, sponsor and proper documentation of the rationale.

#### 4.1.10 DLT, MTD and RP2D definitions

The MTD is defined as the highest dose studied for which the observed incidence of DLT is less than 33%. Frequencies of toxicities will be tabulated according to the NCI Common Toxicity Criteria version 4.03.

The RP2D will be determined based on the safety data and all available correlative data from the escalation phase by the Safety Monitoring Committee.

Dose-limiting toxicity (DLT) is defined as a clinically significant non-hematologic adverse event or abnormal laboratory value assessed as unrelated to disease progression, intercurrent illness, or concomitant medications and is possibly, probably or definitely related to the study drug and occurring during the first cycle (21 days) on study that meets any of the following criteria:

- All Grade 4 non-hematologic toxicities of any duration
- All grade 3 non-hematologic toxicities. Exceptions are as follow:
  - Grade 3 nausea, vomiting and diarrhea that does not require hospitalization or TPN support and can be managed with supportive care to ≤ grade 2 within 48 hours.
  - Grade 3 electrolyte abnormalities that are corrected to ≤ grade 2 within 24 hours

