#### 4.1.7 Dose-escalation

A standard 3+3 dose-escalation design will be used to determine MTD. The potential dose schedule is shown in section 4.1.6. In the first cohort, as a safety precaution, each new subject began treatment only after the safety analysis for DLTs and evaluation of PK data during the first cycle (28 days) was completed for the previous subject. In subsequent cohorts of the dose-escalation phase, new subjects will be entered and treated only after the previous subject has been treated with IACS-010759 for up to 7 days (e.g., has completed the induction phase) and DLT safety analysis for each subject will be performed after completion of cycle 1. PK data will be monitored for each subject and evaluated for each cohort during the study and plasma levels will be considered when making dose escalation decisions.

The following dose-escalation rules will be applied:

- If 0 out of the 3 subjects have a DLT, the next cohort may be started.
- If 1 out of the 3 subjects has a DLT, an additional 3 subjects will be enrolled in the same cohort. If none of these 3 additional subjects have a DLT after being observed for 28 days (i.e., cycle 1), the next dose escalation cohort may be started.
- If 2 or more out of 6 subjects in Cohort 1 develop a DLT, enrollment will cease immediately and the study will be halted. No MTD can be determined.
- If 2 or more out of 6 subjects in the following Cohorts (2-6) develop a DLT, enrollment into the cohort will cease, and the prior cohort's dose level will be deemed as MTD level. All subjects from the non-tolerated cohort will be de-escalated to the prior cohort's dose level.
  - If at least 2 of 3 or 2 of up to 6 patients experience a DLT at a given dose, then the MTD has been exceeded (stopping dose). Once the MTD has been exceeded, treat another 3 patients at the previous dose if there were only 3 patients treated at that dose.

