At the discretion of the sponsor, dose-escalation may be stopped before an MTD is reached. In this case, the RP2D may be chosen based on an assessment of the safety, PK, PD, biomarker, and response data evaluable up to that time. An MTD does not have to be reached to expand a dose cohort if the available data demonstrate that a lower dose level may provide antitumor activity while minimizing potential risk. Upon completion of the dose-escalation, the cohort with either the highest dose level shown to be well tolerated or the RP2D will be expanded to a total of 6 subjects (if not already expanded to 6 subjects due to either observation of a DLT or to further explore safety, PK and PD activity of IACS-010759 at that dose level).

Late onset DLTs that could not be taken into consideration prior to scheduled dose escalations will be ad-hoc evaluated on a case-by-case basis, and may lead to enrollment of additional subjects in specific cohorts or to revision of the previously determined MTD.

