#### 4.1.8 Expansion Phase

Subjects in the expansion phase will be treated at the RP2D level determined in the dose-escalation phase.

The primary objective of the expansion phase is to determine safety of IACS-010759.

Additionally, as part of the expansion phase, the effect of a high fat meal on the PK of IACS-010759 (Food Effect) will be evaluated in a total of 6 subjects (Food Effect cohort), as described in Section 7.1. After the first 6 subjects have been enrolled in the expansion cohort, the next 6 subjects will be enrolled in the Food Effect cohort.

To evaluate safety, the method of Thall, Simon and Estey [20] will be used for monitoring DLTs occurring in the first cycle. The probability of DLT is denoted by  $P_T$ . We assume  $P_T \sim$  beta (0.4, 1.6). Our stopping rule is given by the following probability statement:  $Pr(P_T > 0.20 \mid data) > 0.80$ .

That is, if at any time during the study we determine that there is more than 80% chance that the unacceptable toxicity rate is more than 20% during the expansion phase, then the enrollment will be stopped. Subjects will be monitored by a cohort size of 6 during the expansion phase according to the following stopping boundaries for DLTs, starting from the 12th

subject. The monitoring rule for DLTs, based on these assumptions and monitoring conditions is found in Table 3. For example, accrual in the expansion phase will cease if 4 or more subjects experience DLTs among the first 12 subjects. The operating characteristics are summarized in Table 4. The design software Multc Lean Desktop (version 2.1) developed by the Department of Biostatistics at M. D. Anderson Cancer Center was used to generate the toxicity stopping boundaries and the operating characteristics tables.

Table 3 Stopping boundaries for DLT monitoring

# Subjects evaluated	12	18
# Subjects with DLTs	4-12	6-18

Table 4 Operating characteristics of toxicity monitoring

True DLT Rate	Early Stopping Probability	Average Sample Size
0.10	0.0256	17.8
0.15	0.0922	17.4
0.20	0.2054	16.8
0.25	0.3512	15.9
0.30	0.5075	15.0

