Myelosuppression and associated complication are expected events during leukemia therapy. Only prolonged myelosuppression, as defined as ANC <500 through day 42 or later (6 weeks) from start of therapy without any evidence of leukemia, will be considered in defining the MTD and DLT.

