### 6 Study Drug

### 6.1 Study Drug Administration

Cohorts 1 and 2: For each cycle 1, a single oral dose of IACS-010759 will be administered on day 1. The next dose of IAC-010759 will be administered on day 8, and daily continuously for the duration of the study with no interruptions unless there are adverse events as described in Section 4.1.9. IACS-010759 doses will be separated by intervals of approximately 24 hours (+/- 3 hours).

Cohorts 3-6 and Dose Expansion: Based on the observed accumulation of IACS-010759 throughout the dosing period in cohorts 1 and 2, a modified dosing regimen is being implemented, consisting of an induction phase in which IACS-010759 is administered daily for up to 7 days, followed by a maintenance phase in which a lower dose is administered weekly (or as otherwise specified by the SMC based on safety, PK and PD data observed) to maintain steady state plasma levels. Dosing will proceed on this schedule for the duration of the study with no interruptions unless there are adverse events as described in Section 4.1.9.

IACS-010759 will be administered without food, at least 1 hour before and at least 2 hours after eating. Each dose of IACS-010759 should be administered with 8 ounces of water. If a dose is missed, the next dose will not be increased to account for missing a dose. The subject will take the next regular dose at the scheduled time. Following cycle 1 (28-day cycle for cohorts 1 and 2, 21 day cycle for subsequent cohorts), subjects will receive one cycle of therapy every 21 days (+/- 4 days).

In cohorts 1 and 2, treatment was administered as an inpatient for 24 hours on day 1 and then starting on day 8 for the next 7 days for all enrolled subjects. In cohorts 3 and 4, treatment will be administered as an inpatient for 24 hours on Day 7 of Cycle 1 for all enrolled subjects. In subsequent cohorts, treatment will be administered as an inpatient for 24 hours on Day 5 of Cycle 1 for all enrolled subjects. IACS-010759 will be self-administered and subjects instructed not to dose on days when PK/PD samples are collected until advised by the research staff. Self-administration can occur on days without PK/PD and subjects will record administration in a provided diary.

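### The DLT window is 21 days in Section 4.1.10 and 28 days in Section 4.1.7, neither limited by cohort, and the day-42 hematologic DLT has no stated place in the escalation or expansion counts

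*Combined protocol and SAP*

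**What the plan says.** The DLT window appears in four places in the current protocol text.

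- **Section 4.1.10, definition.** "Dose-limiting toxicity (DLT) is defined as a clinically significant non-hematologic adverse event or abnormal laboratory value", related to study drug and "occurring during the first cycle (21 days) on study that meets any of the following criteria". No cohort is named.
- **Section 4.1.7, the 3+3 rule after 1 DLT in 3.** "If none of these 3 additional subjects have a DLT after being observed for 28 days (i.e., cycle 1"), the next cohort may open. Again no cohort is named.
- **Section 4.1.10, closing paragraph on myelosuppression.** "ANC <500 through day 42 or later (6 weeks) from start of therapy without any evidence of leukemia" is the only myelosuppression that "will be considered in defining the MTD and DLT".
- **Section 4.1.8, expansion phase.** The Bayesian stopping rule "will be used for monitoring DLTs occurring in the first cycle".

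Section 6.1 gives the cycle lengths: "Following cycle 1 (28-day cycle for cohorts 1 and 2, 21 day cycle for subsequent cohorts"). Section 4.1.2 sets DLT monitoring over the first cycle before the next cohort proceeds. Section 4.1.7 adds a safety net: "Late onset DLTs that could not be taken into consideration prior to scheduled dose escalations will be ad-hoc evaluated on a case-by-case basis". Such a review may add subjects or revise the MTD.

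**The concern.** DLTs, the MTD and the RP2D are the primary objective, and the DLT count decides every escalation step. Two parts of the definition do not fit together.

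First, the 21-day figure does not match cycle 1 in cohorts 1 and 2, and the 28-day figure does not match cycle 1 from cohort 3 on. Neither sentence is restricted to the cohorts it fits. An event on days 22 to 28 can therefore be classified either way in any cohort that goes to six subjects, and that can decide whether the cohort is tolerated.

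Second, the only marrow-toxicity DLT in the plan is meant to count towards the DLT and the MTD. As written it sits outside the definition that introduces it, matures after each subject's first-cycle assessment, and is not among the events the expansion rule monitors.

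**Working it through.** **1. The plan's own figures.** The only computed figures that use the DLT count are Tables 3 and 4. With prior beta(0.4, 1.6), the posterior after r DLTs in n subjects is beta(0.4 + r, 1.6 + n − r). Pr(P_T > 0.20) is 0.608 at 3/12, 0.821 at 4/12, 0.747 at 5/18 and 0.883 at 6/18. The 0.80 cut-off is therefore first crossed at 4/12 and 6/18, as in Table 3. Early stopping is q = P(Bin(12, p) ≥ 4), which gives 0.0256, 0.0922, 0.2054, 0.3512 and 0.5075 at p = 0.10 to 0.30, as in Table 4. Average N = 12q + 18(1 − q) also agrees to rounding. The problem is the definition of the event counted, not the arithmetic.

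**2. The 1/6 versus 2/6 case, with no assumption about rates.** Take one DLT in the first three subjects of a cohort from 2 to 6, then one related grade 3 event between days 22 and 28 in an added subject.

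- 21-day window governs: 1/6 = 16.7%, below the 33% limit in Section 4.1.10, so escalate.
- 28-day window governs: 2/6 = 33.3%, not below 33%, and the 2-of-6 rule in Section 4.1.7 declares the MTD exceeded.

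**3. How often it matters.** The documents give no DLT rates or timing for the 3+3 part, so these are assumptions. Let a be the per-subject DLT probability in the first three subjects and b that in the added three.

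P(clear) = (1 − a)³ + 3a(1 − a)²(1 − b)³

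Under a constant hazard, a 28-day rate of 0.30 gives a 21-day rate of 1 − 0.70^0.75 = 0.235.

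- 21 days throughout (a = b = 0.235): 0.448 + 0.185 = 0.63
- 28 days for the added three only, as Section 4.1.7 literally reads (a = 0.235, b = 0.30): 0.448 + 0.141 = 0.59
- 28 days for all six (a = b = 0.30): 0.343 + 0.151 = 0.49

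The same calculation from assumed 21-day rates:

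| 21-day rate | 28-day rate | 21 days throughout | 28 days, added three | 28 days, all six |
|---|---|---|---|---|
| 0.10 | 0.131 | 0.906 | 0.888 | 0.851 |
| 0.20 | 0.257 | 0.709 | 0.669 | 0.584 |
| 0.30 | 0.379 | 0.494 | 0.449 | 0.345 |

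Without constant hazard: at a 21-day rate of 0.20, an extra risk of 0.02 to 0.10 on days 22 to 28 gives 0.665 to 0.494 if 28 days applies to all six. If it applies to the added three only, 0.512 + 0.384(1 − b)³ with b = 0.22 to 0.30 gives 0.694 to 0.644.

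**4. The hematologic criterion.** It cannot be met before day 42, which is 42 − 21 = 21 days after a 21-day window closes and 42 − 28 = 14 days after a 28-day window closes. Section 4.1.7 staggers entry by up to 7 days. With starts on days 0, 7 and 14, the third subject's 21-day assessment falls on day 14 + 21 = 35, before the first subject has reached day 42. If three more then start on days 35, 42 and 49, the last 21-day assessment is on day 70. By then the first three have reached their own day 42 (on days 42, 49 and 56), but the text does not say whether a matured event joins the count. Slower accrual has the same effect.

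**5. The expansion rule.** Suppose, as an assumption, an independent hematologic DLT risk of 0.05 to 0.10 on top of a first-cycle rate of 0.20. Counting both gives 1 − 0.80 × 0.95 = 0.24 to 1 − 0.80 × 0.90 = 0.28. P(Bin(12, p) ≥ 4) is then 0.32 to 0.45, against 0.205 when only first-cycle events count.

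**The case against.** The best defence is that Section 4.1.7 does not define a DLT. It only says how long the added subjects are observed, while Section 4.1.10 defines the event. On that reading a day-24 event in cohort 5 is seen but is not a DLT, and the count is 1/6. The term used throughout is the first cycle, Section 6.1 gives its length, and the 28 days may simply be left over from cohorts 1 and 2. This is a fair reading, and it means the switch in count depends on which section governs. It does not remove the conflict: Section 4.1.7 makes escalation conditional on 28 DLT-free days, equates 28 days with cycle 1, and gives no cohort limit.

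Four stronger readings are tempting, and the documents do not support them.

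- A reader might infer that the hematologic event can never count. The closing paragraph of Section 4.1.10 says it is to be considered, and the late-onset clause allows the MTD to be revised. It is outside the prespecified counts, not lost to the study.
- A reader might infer that its leukemia-free condition cannot be checked because no marrow is scheduled at day 42. In cohorts 3 to 7 hematology is scheduled that day (C2D21). Marrow is scheduled at C1D21 and C3D21, but the flowchart notes also allow it when clinically indicated.
- A reader might infer that different sites would classify differently. There is one site and one Safety Monitoring Committee; the ambiguity is between readers of the text.
- A reader might size the effect by the chance of at most 1 DLT in 6, which is 0.42 with 28 days and 0.57 with 21 days at the 30% rate. That is not the 3+3 rule, which also clears a cohort at 0/3.

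**Conclusion.** The point holds. The current text gives two unreconciled non-hematologic windows, and a single event on days 22 to 28 in an added subject can turn 1/6 into 2/6. That follows from the written rules alone, provided the 28-day sentence is taken to govern. Under the assumed constant hazard and 30% rate, the clearance probability changes by about 4 points if Section 4.1.7 is read literally (0.63 to 0.59) and about 14 points if 28 days applies to all six subjects (0.63 to 0.49). These sizes rest on assumed rates and timing.

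The hematologic DLT is outside the 21-day non-hematologic definition and the first-cycle expansion rule, and each subject's result comes after that subject's cycle-1 assessment. The late-onset clause can reach it, but only case by case, and nothing in that clause feeds Table 3. The practical exposure is in the later cohorts and the expansion phase, since Section 4.1.6 describes dosing in cohorts 1 and 2 in the past tense.

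**What to change.** Reconcile Sections 4.1.7, 4.1.8 and 4.1.10 so that each cohort group has one stated non-hematologic DLT window, used identically in all three. The sponsor chooses its length.

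Take the prolonged-neutropenia criterion out from under the non-hematologic, first-cycle (21 days) definition and give it its own stated window. Then say whether, and from when, a matured day-42 event enters the 2-of-6 count and the Table 3 counts. If it is to enter Table 3, the DLT rate in Table 4 must be read as covering both kinds of event.

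The cost is protocol wording, with no new assessments and no change to sample size. The one downside is that some counts may be updated after a cohort has been read out.

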#### Lactic Acid:

- Blood lactic acid levels [>4.0 mmol/L]) and decreased blood pH (>7.2 to <7.30) and no clinical symptoms of metabolic acidosis [nausea, vomiting, generalized muscle weakness, tachycardia, hypotension and rapid breathing] and normal potassium maintained in two consecutive laboratory assessments separated by >12 hours despite management as described in Section 4.1.11. To qualify as a DLT, the blood lactic acid levels [>4.0 mmol/L]) and decreased blood pH (<7.30) should be confirmed on arterial blood draws. Patients who develop pH between 7.30 - 7.35 while on therapy who are asymptomatic, and have other etiologies for metabolic acidosis ruled out, may be permitted to continue on treatment. These patients will have an increased monitoring of pH and lactate levels minimally at approximately 6 hours, 12 hours and 24 hours, until normalization of pH is established, so as to rule out any worsening acidosis. Patients with a baseline normal pH (>7.35) and no clinical evidence of progressive leukemia (defined by >50% blasts in the bone marrow or peripheral blood, white count >20K, requiring hydroxyurea to control WBC counts, or new extramedullary leukemia) who develop acidosis that fulfills the criteria for a DLT during the DLT window, should be considered a DLT.
- Blood lactic acid levels [>4.0 mmol/L]), decreased blood pH (<7.35 if the

baseline pre-therapy pH was >7.35 or blood pH <7.30 if the baseline pre-therapy pH was  $\leq$ 7.35), with bicarbonate >LLN and anion gap elevated, abnormal potassium and/or, in the opinion of the investigator, the subject is symptomatic for lactic acidosis [nausea, vomiting, generalized muscle weakness, tachycardia, hypotension and rapid breathing (Section 4.1.11, point 3). To qualify as a DLT, the blood lactic acid levels [>4.0 mmol/L]) and decreased blood pH <7.35 if the baseline pre-therapy pH was >7.35 or blood pH <7.30 if the baseline pre-therapy pH was  $\leq$ 7.35), should be confirmed on arterial blood draws.

 Second episode of blood lactic acid level > 4.0 mmol/L, confirmed as lactic acid level > 4.0 mmol/L on arterial blood, separated by >24 hours blood draw, in the presence of clinical symptoms attributable to lactic acidosis [nausea, vomiting, generalized muscle weakness, tachycardia, hypotension and rapid breathing]

Myelosuppression and associated complication are expected events during leukemia therapy. Only prolonged myelosuppression, as defined as ANC <500 through day 42 or later (6 weeks) from start of therapy without any evidence of leukemia, will be considered in defining the MTD and DLT.

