- 2. If lactic acid >ULN but below 4.0 mmol/L, and subject is symptomatic (nausea, vomiting, generalized muscle weakness, tachycardia, hypotension and rapid breathing), treatment should be interrupted as indicated and lactic acidosis workup performed.
- 3. If lactic acid is above 4.0 mmol/L, blood pH ≥7.35 and bicarbonate (reported as total CO2) is <LLN, potassium is normal and anion gap <14, and subject is asymptomatic, dosing should be interrupted. Lactic acid and blood pH and electrolytes should be reassessed within 12 hours on arterial and/or venous blood draw until the lactic acid level is <4.0 mmol/L. Once the lactic acid level is <4.0 mmol/L on arterial and/or venous draw, the subject can continue therapy at the discretion of the investigator.
- 4. If lactic acid is above 4.0 mmol/L, blood pH <7.35 if the baseline pre-therapy pH was >7.35 or blood pH <7.30 if the baseline pre-therapy pH was ≤7.35) and the bicarbonate (reported as total CO₂) is <LLN and anion gap is elevated, and/or the subject is symptomatic, this will be considered a DLT. Treatment should be interrupted and lactic acidosis workup performed (See Section 7.2.3).

Anion gap via venous blood collection can be calculated as follows: Anion Gap= [Na+] - [Cl-] - [total CO2]; normal range 4-14 mmol/L.

Anion gap via arterial blood collection can be calculated as follows: Anion Gap= [Na+] - [Cl-] - [HCO3-]; normal range 8-16 mEq/L.

Symptoms of lactic acidosis include nausea, vomiting, generalized muscle weakness, tachycardia, hypotension and rapid breathing. Subjects with clinical symptoms concerning for lactic acidosis should have an arterial blood gas assessment. Lactic acidosis is characterized by an elevated blood lactate concentration [>4.0 mmol/L]), decreased blood pH (<7.35), and electrolyte disturbances with an increased anion gap.

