### 7.2.3 Lactic Acidosis and Severe Acidemia Management

Subjects with lactic acidosis and severe acidemia (pH < 7.1) should be seen by a nephrology specialist as soon as possible and receive bicarbonate therapy. When using bicarbonate therapy in subjects with lactic acidosis and severe acidemia, the aim is to maintain the arterial pH above 7.1. Rapid infusions of sodium bicarbonate may increase the pCO2, accelerate the production of lactate, lower the ionized calcium, expand the extracellular space, and raise the serum sodium concentration. There is little evidence that any alternative buffering agents are superior to bicarbonate therapy. In adequately ventilated subjects with lactic acidosis and severe acidemia, 1 to 2 mEq/kg sodium bicarbonate is given as an intravenous bolus. This dose is repeated after 30 to 60 minutes if the pH is still below 7.1.

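### The first lactic-acid DLT criterion in Section 4.1.10 states two incompatible pH conditions, one of which leaves out pH 7.2 or lower, and the neighbouring rules close that gap only in part

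*Combined protocol and SAP*

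**What the plan says.** Section 4.1.10 defines a DLT as a clinically significant, at least possibly drug-related, first-cycle non-hematologic event or laboratory value "that meets any of the following criteria". The criteria are therefore alternatives. Those relevant here are:

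- **First lactic-acid bullet.** Lactate above 4.0 mmol/L with "decreased blood pH (>7.2 to <7.30) and no clinical symptoms of metabolic acidosis", and "normal potassium maintained in two consecutive laboratory assessments separated by >12 hours" despite the management in Section 4.1.11. Its confirmation sentence reads "the blood lactic acid levels [>4.0 mmol/L]) and decreased blood pH (<7.30) should be confirmed on arterial blood draws".
- **Second lactic-acid bullet.** Lactate above 4.0 mmol/L with pH below 7.35 or below 7.30, depending on baseline and with no lower limit, "with bicarbonate >LLN and anion gap elevated, abnormal potassium and/or, in the opinion of the investigator, the subject is symptomatic for lactic acidosis". It refers the reader to Section 4.1.11 point 3.
- **Third lactic-acid bullet.** A second episode of raised lactate, with symptoms.
- **General criteria.** All Grade 4 and all Grade 3 non-hematologic toxicities. The Grade 3 exceptions are certain gastrointestinal events and corrected electrolyte abnormalities.

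Section 4.1.11 adds two cases. Point 3 describes raised lactate with pH 7.35 or higher and no symptoms; dosing is interrupted, and a DLT is not mentioned. Point 4 uses the same baseline-dependent pH limits as the second bullet, but with bicarbonate below the lower limit of normal (LLN), and continues: "anion gap is elevated, and/or the subject is symptomatic, this will be considered a DLT".

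**The concern.** A toxicity rule that feeds a dose-finding design should not reverse with severity: if a value counts as a DLT, a worse value of the same measurement, all else equal, should count too. Read literally, the first bullet breaks this. It has a lower as well as an upper pH limit, so a subject at 7.28 is inside and a subject at 7.15 is outside. The confirmation sentence in the same bullet has no lower limit, and nothing in the text explains the difference or directs lower values to another criterion.

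Lactic acidosis is the mechanism-based effect that Section 4.1.11 names, and Section 7.2.3 foresees values well below 7.2: "Subjects with lactic acidosis and severe acidemia (pH < 7.1) should be seen by a nephrology specialist". That passage is treatment guidance and does not bear on DLT counting, but it shows that the range is not hypothetical to the authors.

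DLT status drives the 3+3 steps (Section 4.1.7), the MTD (4.1.10), the expansion stopping rule (4.1.8), permanent discontinuation for lactic-acid DLTs (4.1.9) and eligibility for intra-subject escalation (4.1.9.3).

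**Working it through.** There is no planned figure to reproduce; the check is one of logic.

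**Fixed conditions.** Lactate above 4.0 mmol/L confirmed on arterial blood, abnormality persisting more than 12 hours, baseline pH above 7.35, first episode. pH is set to 7.25, 7.20 and 7.15. Symptoms, potassium, bicarbonate (below or above LLN) and anion gap (elevated or not) are varied, giving 2 × 2 × 2 × 2 = 16 profiles.

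**Rules.**

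- Bullet 1 as written: 7.2 < pH < 7.30, no symptoms, normal potassium.
- Bullet 1 using its confirmation sentence: pH < 7.30, otherwise the same.
- Bullet 2 under three readings. (A) Bicarbonate above LLN, elevated gap and abnormal potassium together; or symptoms. (B) Bicarbonate above LLN and elevated gap, with either abnormal potassium or symptoms. (C) Bicarbonate above LLN with elevated gap; or abnormal potassium; or symptoms.
- Section 4.1.11 point 4: bicarbonate below LLN with elevated gap; or symptoms.
- Bullet 3 cannot apply, because this is a first episode.

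**Where a reversal is possible.** Bullet 1 is the only rule whose answer changes between 7.25 and 7.20, and it applies only without symptoms and with normal potassium. The other 12 profiles give the same answer at all three pH values. The 8 symptomatic ones are DLTs throughout under point 4. That leaves four profiles. All four are DLTs at pH 7.25 through bullet 1. At 7.20 and 7.15:

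| Bicarbonate | Anion gap | Bullet 1 as written | Bullet 2 | 4.1.11 point 4 | Reversal across lactic rules |
|---|---|---|---|---|---|
| Below LLN | Elevated | No | No (A, B, C) | Yes | None |
| Below LLN | Not elevated | No | No (A, B, C) | No | Remains |
| Above LLN | Elevated | No | Only under C | No | Depends on bullet 2 |
| Above LLN | Not elevated | No | No (A, B, C) | No | Remains |

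With the confirmation sentence's condition in bullet 1, all four profiles are DLTs at all three pH values.

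**Section 4.1.10's lactic bullets alone.** Without point 4, three of the four profiles reverse under every reading of bullet 2, and the fourth depends on the reading. Point 4 reduces the certain reversals from three to two.

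**Point 4 against bullet 2.** They share lactate and pH conditions but require bicarbonate in opposite directions: above LLN in bullet 2, below LLN in point 4. Bullet 2 cites point 3, whose pH of 7.35 or higher and absence of symptoms do not match bullet 2.

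**What one classification can change.** Under Section 4.1.7, 1 DLT in 3 means three more subjects, while 0 in 3 allows the next cohort. With six subjects, 2/6 = 33.3% means the MTD is exceeded, while 1/6 = 16.7% does not. In Section 4.1.8, 4 of 12 stops accrual and 3 of 12 does not.

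**The case against.** The strongest reply is that Sections 4.1.10 and 4.1.11 must be read together, since the first two bullets both refer to 4.1.11. Point 4 then catches the picture that 4.1.11 itself gives of lactic acidosis: raised lactate, low pH and an increased anion gap. If bicarbonate is also below LLN, the subject is a DLT at any low pH, with or without symptoms. This stands, and it makes the gap narrow. A subject at pH 7.15 whose bicarbonate and anion gap are unstated cannot be said to escape.

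The general Grade 3 and 4 criteria also have no pH limit, and acidosis is not a listed exception. The requirement of clinical significance is in the lead-in, so it applies equally to the first bullet and is no extra hurdle. Section 8.1.1 makes a laboratory result that leads to withheld treatment an adverse event, and the Section 8.1.3 grading relief for observation in hospital applies only if pH remains normal. This route may well work. The documents do not say how a pH of 7.2 or lower is graded, so it can be neither relied on nor dismissed.

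A reader might infer that the most severe acidosis is not a DLT and that the dose causing it would be cleared. The documents do not support that. It would require point 4, bullet 2 and the general criteria all to fail for the same subject. Even after 0 of 3, Section 4.1.7 only permits the next cohort, under Safety Monitoring Committee review.

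What the reply does not answer is the contradiction inside the first bullet, or the fact that point 4 conflicts with bullet 2 on bicarbonate.

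**Conclusion.** The point holds as an internal contradiction in the primary-endpoint rule, with a narrow residual gap. The first bullet gives two pH conditions that disagree for every value of 7.2 or lower. Under the literal range, DLT status reverses within that bullet. Across all lactic-specific rules the reversal clearly remains only for asymptomatic, normal-potassium subjects without an elevated anion gap. With bicarbonate above LLN and an elevated gap it depends on how bullet 2's and/or is read. It does not arise with bicarbonate below LLN and an elevated gap, or in symptomatic subjects.

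The two-of-four count is of logical profiles, not of patients. The documents give no frequency, and subjects with a normal anion gap do not match the protocol's own description of lactic acidosis. The result assumes a persistent, arterially confirmed abnormality in a first episode, and leaves the Grade 3 and 4 route open. Point 4's and/or was read as making symptoms sufficient alone; a narrower reading would not change the table, which concerns asymptomatic subjects only.

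The matter deserves correction despite its narrowness because a single disputed classification can change a cohort decision, the MTD or a subject's discontinuation.

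**What to change.** The passages must be reconciled by amendment. The choice of threshold is the sponsor's.

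1. In the first lactic-acid bullet of Section 4.1.10, make the pH condition in the criterion and the one in the arterial-confirmation sentence agree. If pH 7.2 or lower is meant to fall under another criterion, name it.
2. Reconcile the second bullet with Section 4.1.11 points 3 and 4: the direction of the bicarbonate condition, the cross-reference to point 3, and the grouping of the conditions joined by and/or.
3. State whether and how the general Grade 3 and 4 criteria apply to low blood pH.
4. Check the reconciled text for consistency: with all other findings equal, a lower pH must never turn a DLT into a non-DLT.

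The cost is a text amendment. Lactate, blood pH and electrolytes are already collected under Section 4.2, so no procedure, visit or sample is added.
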